4.2 Exclusion Criteria

- Inability to understand and write in the English language
- Unable to participate due to other factors, as assessed by the Chief Investigators
- Pregnant women

4.3 Withdrawal criteria

- Loss of capacity to give informed consent
- Investigator initiated discontinuation of study due to participation concerns

Withdrawal will be immediate, and participants will be followed up in the appropriate out-patient diabetes clinic at their usual appointments. If a participant withdraws no more data will be collected on them but identifiable data already collected with consent will be retained and used in the study.

If a participant, who has given informed consent, loses capacity to consent during the study the participant will be withdrawn from the study. Identifiable data already collected with consent will be retained and used in the study. No further data would be collected or any other research procedures carried out on or in relation to the participant.

5. ADVERSE EVENTS

5.1 Definitions

Adverse Event (AE): any untoward medical occurrence in a patient or clinical study subject.

Serious Adverse Event (SAE): any untoward and unexpected medical occurrence or effect that:

- **Results in death**
- **Is life-threatening** – refers to an event in which the subject was at risk of death at the time of the event; it does not refer to an event which hypothetically might have caused death if it were more severe
- **Requires hospitalisation, or prolongation of existing inpatients' hospitalisation**
- **Results in persistent or significant disability or incapacity**
- **Is a congenital anomaly or birth defect**

Medical judgement should be exercised in deciding whether an AE is serious in other situations. Important AEs that are not immediately life-threatening or do not result in death or hospitalisation but may jeopardise the subject or may require intervention to prevent one of the other outcomes listed in the definition above, should also be considered serious.

5.2 Reporting Procedures

All adverse events should be reported. Depending on the nature of the event the reporting procedures below should be followed. Any questions concerning adverse event reporting should be directed to the Chief Investigator in the first instance.

5.2.1 Non serious AEs

All such events, whether expected or not, should be recorded.

5.2.2 Serious AEs

An SAE form should be completed and faxed to the Chief Investigator within 24 hours. However, relapse and death due to diabetes mellitus, and hospitalisations for elective treatment of a pre-existing condition do not need reporting as SAEs.

All SAEs should be reported to the Cornwall and Plymouth REC where in the opinion of the Chief Investigator, the event was:

- ‘related’, i.e. resulted from the administration of any of the research procedures; and
- ‘unexpected’, i.e. an event that is not listed in the protocol as an expected occurrence

Reports of related and unexpected SAEs should be submitted within 15 days of the Chief Investigator becoming aware of the event, using the NRES SAE form for non-IMP studies. The Chief Investigator must also notify the Sponsor of all SAEs.

Local investigators should report any SAEs as required by their Local Research Ethics Committee, Sponsor and/or Research & Development Office.

Contact details for reporting SAEs

[contact]

CI email (and contact details below)

[contact], attention [name]

Please send SAE forms to: Diabetes, Endocrinology and Metabolism Medicine, Imperial College London, [name]

[contact] (Mon to Fri 09.00 – 17.00)

6. ASSESSMENT AND FOLLOW-UP

The main study will consist of completing a survey and some questionnaires. This should take no more than 1 hour to complete by the participant at a time and location convenient to them. Participants will be invited to consent to be contacted for the optional sub-study which will be described later in this section.

All eligible participants will be identified by the clinical care team. A list of potential participants will be identified from the database of all people who attend the diabetes clinics at Imperial College Healthcare NHS Trust (subsequently known as the participant database). Additionally, eligible participants from the list of non-Imperial research consenters will also be contacted about the study.

Potential participants will be contacted in one of three ways by the clinical team:

- a) Participants whose emails are available on Cerner or who are not Imperial patients but have consented to contact for research will be contacted by email by a member of the research team. The email will include the PIS and a link to Qualtrics (an online data collection platform which is supported by the college). Informed consent will be taken via this platform with questionnaires to follow (only accessible if participant has consented to all clauses and signed electronically). Participants will be able to arrange a phone call with the research team to discuss any issues or concerns before signing the consent if they wish. Participants who attend clinics at Imperial College Healthcare NHS Trust will be provided with a unique code to enable researchers to link their questionnaire data with their medical records. This will be different to the study code and which will be assigned to participants after consent in order of enrolment.
- b) For potential participants whose emails are not available or who prefer a hard copy approach, study packs, including the patient information sheet, consent form and questionnaire will be sent by post for completion at home, and returned in a pre-paid addressed envelope to the research team.
- c) Patients who are seen in clinic by the diabetes team will be approached by their clinical team about participating in the study. Those who are interested will then be provided with a consent form and study questionnaire which can either be completed and returned to the research team whilst in the clinic or taken home and returned in a stamped addressed envelope at the participant's convenience.

Of the participants who are enrolled in the study, and who have consented to be contacted for an interview, the research team plans to select approximately 16 participants to take part in the qualitative interview. Participants will be selected based on clinician identification and participant self-identification of fear of hyperglycaemia, as well as from a dynamic list of those in the upper quadrant of recorded scores on the Hyperglycaemia Avoidance Scale.

Participants will be advised that questionnaires should be returned by the end of the study for inclusion in the study analysis.

Within the patient information sheet there will be contact details for the research team, should the participant wish to discuss the study and obtain any further details.

Once returned, the pseudonymised questionnaire data will be recorded in a password encrypted database on an Imperial College Healthcare NHS Trust or Imperial College London computer (subsequently known as the results database). Informed consent will be filed in the trial master file.

Once informed consent has been provided, the research team will then review the electronic health records of those Imperial College Healthcare NHS Trust participants who have consented to record biochemical data, medical history. Other baseline data e.g. demographics will be collected via a participant survey which will be mailed alongside questionnaires. This data will be recorded in pseudonymised form in the results database. Data from Qualtrics will be downloaded in a PDF format on either an ICL or ICHT computer and printed for hard copy records. Questionnaire scoring data will be pulled from Qualtrics in a pseudonymised format and saved on either an ICL or ICHT computer within an encrypted, password protected document.

In all cases, no samples are taken and all data will be pseudonymised. No follow up outside of usual care will be provided.

If participants wish to see their questionnaire scores, they will be able to request this. They will be sent a standardised letter including their scores on each measure and, where available, what this score is suggestive of (e.g. mild depression). Some of the measures do not have standardised cut-offs. This will only be sent if requested and not for all participants.

Any participant who scores in the severe range on the GAD-7 (scores of 15-21) or the PHQ-9 (scores of 20-27), or who scores 3 on question 9 of the PHQ-9 (this question relates to thoughts of harm to self) will have a letter sent to their GP advising them of this, and the participant will receive a copy.

Any disclosure made to the researchers that constitutes a safeguarding issue, or a potential risk to self or others, will be shared with the clinical team and managed appropriately as per the usual clinical care pathway, including contacting other agencies where indicated. Where participants report mental health problems such as anxiety or depression, based on the Clinical Psychologist's judgement, they will be signposted or, where appropriate, referred, to appropriate mental health services as is usual practice in their clinical care. This might include, for example: their local mental health trust's Single Point of Access; Improving Access to Psychological Therapies (IAPT); the London-wide Type 1 Disordered Eating Service.

If the participant raises concerns that they do not wish to be shared with their clinical care team, but the researcher feels should be shared, an anonymised discussion will be initiated with the Principal Investigator, and if appropriate, the clinical care team. The Trust Ethics Committee can also be consulted, if appropriate, to consider what is in the participant's best interests.

Participants' GPs will not be informed of their participation in the study as it will not affect their care.

End of study will be defined as last subject last visit (LSV).

Sub-study – Qualitative semi-structured interview

Of the participants who are enrolled into the study (and who have consented to be contacted for an interview) the research team plan to select approximately 16 whose HAS scores are relatively higher than other participants in order to conduct a qualitative semi-structured interview. This will be judged from previous research and participants who score in the upper quartile of the entire measure. (Singh *et al.*, 2014). Participants of varying backgrounds will be selected to ensure a mix of demographics, diabetes duration, HbA1c etc. This is in order to ensure a heterogeneous pool of participants to inform our hypothesis.

Participants will not be reconsented to take part in the interview study as they will have already opted in on the original consent form, having read the PIS which details this sub study. The

interviews will take place either remotely via Microsoft teams or face to face at St Mary's hospital.

An inductive, exploratory approach will be taken to learn more about fear of hyperglycaemia. An initial semi-structured interview schedule will be used to guide the interviews and, in line with the grounded theory approach, the information gathered from interviews will be used to shape and inform subsequent participant interviews as hypotheses and theories are developed. The interview will be conducted by a clinical psychologist, will last a maximum of 90 minutes and will be recorded and then transcribed verbatim by the clinical psychologist.

The audio recording will be anonymous and will be destroyed once the interview has been transcribed. The interview will be transcribed in pseudonymous format. After the interview, the clinical psychologist will email the participant with the themes that they identified during the interview. This is called a credibility check and the participant will be asked to respond with confirmation that they agree/disagree with the themes that have been outlined. A third party (who will be an appropriately qualified member of the research team employed under ICHT) will review the pseudonymised transcripts and provide feedback. This is the second part of the credibility check. This third party will not have access to the identifiable codes.

The psychologist is experienced in sensitively discussing difficult and distressing topics with individuals and will routinely debrief all participants at the end of each interview. If during the course of interviews, individuals disclose actual or possible risk of harm to self or others, this will be assessed and managed using the same procedures that are used in a clinical setting.

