8.3 Confidentiality

Anonymised quotes may be used in publications if the participant has given written informed consent. The Chief Investigator will preserve the confidentiality of participants taking part in the study and is registered under the Data Protection Act.

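### As worded, the online consent rule makes main-study entry depend on agreeing to interview contact, although the interview sub-study is optional

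*Combined protocol and SAP*

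**What the plan says.** All the relevant text is in the combined protocol and SAP.

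- **Access rule.** Section 6, contact route (a), takes consent on Qualtrics. The questionnaires that follow are "only accessible if participant has consented to all clauses and signed electronically".
- **Status of the interview.** The opening paragraph of Section 6 says: "Participants will be invited to consent to be contacted for the optional sub-study".
- **Where the opt-in is recorded.** The sub-study part of Section 6 says: "Participants will not be reconsented to take part in the interview study as they will have already opted in on the original consent form".
- **Interview consent as an added condition.** Section 4.1, Section 6 (main text and sub-study part) and Section 7 all describe the interview candidates as enrolled participants who have, in addition, agreed to be contacted.
- **Safeguards.** Route (a) adds: "Participants will be able to arrange a phone call with the research team to discuss any issues or concerns before signing the consent". Route (b) covers people with no email on record and those who prefer hard copy. For them, "study packs, including the patient information sheet, consent form and questionnaire will be sent by post for completion at home".

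**The concern.** The access rule requires every clause to be accepted. The interview opt-in is on the form to which that rule applies, yet the sub-study is described as optional. An optional item cannot also be a condition of entry.

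Two things are at stake if the form is built from the sentence as it stands.

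1. **Who is in the online sample.** It would contain only people prepared to be contacted for interview. The primary objective is how problematic fear of hyperglycaemia is, and the interviews explore the same subject, so willingness to be interviewed could be related to the questionnaire scores. The documents do not show that it is, and no direction of bias is claimed.
2. **What the opt-in means.** The protocol describes no second consent before a recorded interview of up to 90 minutes. If ticking the item is also the price of reaching the survey, some ticks may not express a wish to take part.

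**Working it through.** The plan gives no figure on this point, so the check is a comparison of texts.

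1. **Route (a), Section 6.** Access to the online questionnaires requires agreement to every clause plus an electronic signature. No clause is exempted.
2. **Sub-study part of Section 6.** The interview opt-in is on the original consent form. If it counts as one of that form's clauses, step 1 applies to it.
3. **Steps 1 and 2 together.** Online access then requires agreement to interview contact. A person who declines is left with three possibilities: stay out, agree unwillingly, or find another route.
4. **Opening of Section 6.** Participants are invited to agree to contact for an optional sub-study. An invitation that can be declined only by giving up access to the main questionnaires does not fit that description.
5. **Sections 4.1, 6 and 7.** Interview candidates must meet two conditions: being enrolled, and having agreed to contact. Under step 3 the second condition adds nothing for anyone who enrols online, because the first already implies it. The repeated two-part wording therefore suggests that people who decline contact were meant to be able to enrol.
6. **Sub-study part of Section 6, again.** Participants are not consented again for the interview. The item in step 2 is thus the only interview consent that the protocol describes.

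**Size.** Number affected = (number approached online) × (share of them who would decline interview contact). Section 7 says that approximately 350 people have been identified, but it does not split them by contact route. No decline rate is given anywhere. With both factors missing, no number or range follows from the documents.

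**The case against.** The strongest reply is that the conflict depends on material nobody reading the protocol can see. It arises in practice only if the interview item is one of the clauses that must be accepted, and not a separate tick-box. The consent form and the Qualtrics build would settle this, and neither is in the documents. The surrounding text also points to a harmless meaning: the sub-study is called optional before route (a) is described, and agreement to contact is repeatedly treated as additional to enrolment. On that reading the phrase simply means all clauses needed for the main study.

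Much of this stands. The harmless meaning is the likely intent, and the documents do not show that anyone is blocked. What remains is that the sentence does not say what was probably meant. Someone building or auditing the online form from it could shut out people who decline.

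The safeguards also count. A person with doubts can arrange a call before signing, anyone may ask for hard copy, and Section 8.2 protects the right to refuse without giving reasons. These limit the effect, but they do not reconcile the text. Nothing says that a person stopped online would be told of the paper route.

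A reader might go further and infer that entry is conditional online but not on paper, so that selection differs between routes. The documents do not support this. Routes (b) and (c) say how the forms are delivered; in clinic, for example, "Those who are interested will then be provided with a consent form and study questionnaire". They are silent on which clauses must be accepted before the data are used, and a paper pack cannot be locked in any case. Silence does not show that a paper form with one item declined would be accepted.

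**Conclusion.** The inconsistency of wording is real, and its severity is minor. As written, route (a) makes interview contact a condition of online entry to the main study, against the optional status given to the interview elsewhere in the protocol. If applied literally, it would restrict the online sample to people willing to be contacted and weaken the only interview consent described.

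This rests on two assumptions: that the interview opt-in is one of the clauses to be accepted, and that the online form follows the sentence literally. Neither can be confirmed, and the second is probably not what the authors intended. The number of people affected cannot be estimated.

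A reader might also infer that the review of health records is a further optional clause caught by the same rule, because Section 6 limits it to "those Imperial College Healthcare NHS Trust participants who have consented to record biochemical data, medical history". That phrase more naturally means participants who have consented to the study, whose records are then reviewed to obtain those data. The sentence opens by referring to informed consent already given. It is not evidence of a second optional item.

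**What to change.** - **Reword the access rule in Section 6, route (a).** It should say that the questionnaires open once the participant has agreed to all main-study clauses and signed electronically, that the interview-contact item is a yes/no choice, and that either answer gives access.
- **Put the same yes/no item on the paper consent form.** The opt-in then means the same thing however a person enrols.
- **Confirm that the Qualtrics setting matches the new sentence.** If the form already lets people decline and continue, only the protocol text needs to change.

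**Cost.** The work is one sentence, one check of the online setting and one check of the paper form. An amendment step may be needed, because Section 8.1 records that REC and HRA approval has already been obtained. The pool of people who opt in may become somewhat smaller, from which about 16 are to be interviewed. In return, each opt-in would record a free choice.

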2. STUDY OBJECTIVES

Primary Objective

Assess how problematic fear of hyperglycaemia is in T1D

Secondary Objectives

Identify whether fear of hyperglycaemia is associated with any clinical factors

Identify the psychological factors that underpin fear of hyperglycaemia

Assess how fear of hyperglycaemia affects self-management of T1D

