3. STUDY DESIGN

Non-interventional, cross-sectional questionnaire study in adults with T1D

1 hour per participant, 9 months total

n=up to 350 participants total

Sub study of approximately n=16 participants for semi-structured interviews (1.5 hours per participant)

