3.1 Study Outcome Measures

1. Quantitative data:

- a. Hyperglycaemia avoidance scale (HAS)
- b. Hypoglycaemia fear survey (HFS-II)
- c. Problem areas in diabetes scale 5 (PAID-5)
- d. Patient health questionnaire (PHQ-9)
- e. Generalised anxiety disorder scale (GAD-7)
- f. State trait anxiety inventory (Trait subscale)

2. Descriptive data – semi-structured interview

Additional baseline participant data to be pulled from Cerner/via participant survey:

- Age
- Ethnicity
- Length of diabetes
- Current diabetes treatment
- Diabetes complications: nephropathy, neuropathy, retinopathy, cardiovascular disease
- Recent HbA1C
- Other medical conditions
- Other medications
- Hypos – frequency/severity
- Blood glucose monitoring - method and frequency

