4. PARTICIPANT ENTRY

4.1 Pre-registration evaluations

Potential participants will be identified by the clinical diabetes team from the list of people who attend the diabetes clinics at Imperial College Healthcare NHS Trust. Participants with type 1 diabetes who do not attend an Imperial College Healthcare NHS Trust diabetes clinic who have consented to be contacted by the Imperial diabetes research team for research purposes will also be invited to participate in the study.

Of the participants who are enrolled in the study, and who have consented to be contacted for an interview, the research team plans to select approximately 16 participants to take part in the qualitative interview. Participants will be selected based on clinician identification and participant self-identification of fear of hyperglycaemia, as well as from a dynamic list of those in the upper quadrant of recorded scores on the Hyperglycaemia Avoidance Scale.

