7. STATISTICS AND DATA ANALYSIS

Approximately 350 participants have been identified. This includes people who attend the Imperial College Healthcare NHS Trust diabetes clinics, and people who have given the Imperial diabetes research team their consent to be contacted for research. Approximately 16 potential participants will be enrolled into the interview sub-study. This is based on the number estimated to be required to identify no new themes (i.e. reach saturation).

Of the participants who are enrolled into the study (and who have consented to be contacted for an interview) the research team plan to select approximately 16 whose HAS scores are relatively higher than other participants in order to conduct a qualitative semi-structured interview. This will be judged from previous research and participants who score in the upper quartile of the entire measure. (Singh *et al.*, 2014). Participants of varying backgrounds will be selected to ensure a mix of demographics, diabetes duration, HbA1c etc. This is in order to ensure a heterogeneous pool of participants to inform our hypothesis.

This study contains both descriptive and quantifiable data. The quantitative outcomes may be either ordinal or categorical, and proportions tests, including Chi squared tests, t-tests and ANOVAs will be used to determine differences between these outcomes.

The descriptive data will be tabulated and presented as such without statistical analysis. Interviews will be audio-recorded and transcribed verbatim. They will be analysed using a grounded theory approach (Corbin & Strauss, 1990), which aims to develop a set of concepts that provide a theoretical explanation of the phenomenon being studied. Analysis will take place alongside data collection, as it will inform and direct subsequent interviews. Credibility checks (Elliott, Fischer & Rennie, 1999; Stiles, 1993) will involve a third-party examining sections of analysed interview transcripts and providing feedback. In addition to this the researcher will contact the interview participant participants to check the themes with the interview participant and providing feedback.

All personal details will be sent via encrypted email (nhs.net).

Record linking participant information to study ID will be stored securely on an Imperial College NHS trust Computer. All study data will be stored in a pseudonymised format in an encrypted database on an Imperial College NHS trust computer OR Imperial College London computer.

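### The in-clinic recruitment route has no consecutive-offer rule and no recorded route or clinician-identification field, so preferential enrolment of recognised fear-of-hyperglycaemia cases could raise the HAS results unchecked

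*Combined protocol and SAP*

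**What the plan says.** - **Objective and size.** The primary objective (section 2) is: "Assess how problematic fear of hyperglycaemia is in T1D". HAS heads the list of quantitative measures in section 3.1. Section 3 gives "n=up to 350 participants total", and section 7 gives the basis: "Approximately 350 participants have been identified".
- **Sampling list.** Section 6 says: "A list of potential participants will be identified from the database of all people who attend the diabetes clinics". Non-Imperial people who agreed to research contact are added. Route (a) is email with an online form, route (b) is a postal pack, and route (c) is the clinic.
- **Route (c).** "Patients who are seen in clinic by the diabetes team will be approached by their clinical team about participating in the study". Forms may be completed in the clinic or taken home. No order of approach, log of those approached or declining, or limit by route is stated.
- **Interviewees.** Section 4.1, repeated in section 6, draws about 16 from this group: "Of the participants who are enrolled in the study, and who have consented to be contacted for an interview". It then says: "Participants will be selected based on clinician identification and participant self-identification of fear of hyperglycaemia", and adds those with high HAS scores. The sub-study text at the end of section 6, repeated in section 7, selects on high HAS score and a mix of backgrounds. It does not mention clinician identification.
- **Recorded data.** The list in section 3.1 headed "Additional baseline participant data to be pulled from Cerner/via participant survey" covers demographic, diabetes and treatment items. It includes neither recruitment route nor a clinician-identification flag. Section 7 plans no analysis by route.

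**The concern.** The service that makes the clinic approach is also a source of names for the interviews, and survey enrolment is the only way into an interview. Section 1.1 says the authors already see this problem in their clinics, so some cases are probably known to staff. With no rule on whom to approach, staff may encourage recognised cases more than other attendees, either as a first invitation or as a personal prompt to someone already emailed or sent a pack.

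If that happened, the survey would hold more high scorers than the clinic population does, and any HAS mean or share of high scorers would read too high. The secondary objectives are exposed too. Section 1.1 notes that the problem can be missed when HbA1c looks satisfactory. Recognised cases may therefore differ from unrecognised ones, and over-representing them could distort associations between HAS and clinical factors. Without route and prior identification on record, the analyst could neither show the effect nor rule it out.

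**Working it through.** **The plan's own figure.** The 350 is a count of people identified. The documents give no alpha, power, SD, HAS cut-off, precision target or expected response, so there is no calculation to reproduce. For context, the worst-case 95% half-width for a proportion at 350 is 1.96 × √(0.25/350) = 5.2 percentage points.

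**Inputs.** From the documents: 350 identified. Assumed: k = 20 recognised cases, all of whom enrol; d = 1.0 to 1.5 SD above average on HAS; n = 150 or 350 returns; HAS roughly normal with SD 1.

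**Upper end: all 20 are surplus to an otherwise representative sample.** Mean shift = (k/n) × d.
- n = 150: 20/150 × 1.0 = 0.13 SD; 20/150 × 1.5 = 0.20 SD. Half-width 1.96/√150 = 0.16 SD.
- n = 350: 20/350 × 1.0 = 0.06 SD; 20/350 × 1.5 = 0.09 SD. Half-width 1.96/√350 = 0.105 SD.

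**Lower end: the 20 belong to the 350 identified and would have been invited anyway.** If they sit d above the average of all 350, the other 330 average −20d/330 = −0.0606d. Suppose all 20 return, and the remaining returns are representative of the 330.
- n = 150: [20d − 130 × 0.0606d]/150 = 0.081d, so 0.08 to 0.12 SD.
- n = 350: everyone identified has returned, so the shift is zero.

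**Share above the true 75th percentile (25% if unbiased).** For a recognised case, P(Z > 0.6745 − d) = 0.628 at d = 1.0 and 0.795 at d = 1.5.
- Surplus, n = 150: (130 × 0.25 + 20 × 0.628)/150 = 30.0%; with 0.795, 32.3%.
- Surplus, n = 350: (330 × 0.25 + 20 × 0.628)/350 = 27.2%; with 0.795, 28.1%.
- Within the 350: the share among the other 330 is (87.5 − 20 × 0.628)/330 = 22.7%, or 21.7% with 0.795. At n = 150 the observed share is then (130 × 0.227 + 20 × 0.628)/150 = 28%, or 29%. At n = 350 it is 25%.
- Half-widths, 1.96 × √(0.25 × 0.75/n): 6.9 points at 150 and 4.5 points at 350.

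| Returns | Mean shift, SD | Half-width, SD | Share above 75th percentile | Half-width, points |
|---|---|---|---|---|
| 150 | 0.08 to 0.20 | 0.16 | 28% to 32% | 6.9 |
| 350 | 0 to 0.09 | 0.105 | 25% to 28% | 4.5 |

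The half-widths only give scale. A confidence interval does not allow for a shift of this kind.

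**What excluding the recognised cases would do.** If the 20 belong to the 350, the remaining 330 average 0.06 to 0.09 SD below the true mean, with 22% to 23% above the 75th percentile. Exclusion therefore errs downward.

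**The case against.** The strongest reply is that the documents describe no selection by staff. A reader might infer that clinicians choose whom to approach, or that a clinician with a promising interviewee has to recruit that person. Neither is stated. Route (c) reads as an approach to patients seen in clinic, and clinician identification is described for people already enrolled. The later interview text omits it. An upper quartile of HAS scores would give about 37 people at 150 returns (150/4) and 87 at 350 (350/4), before allowing for consent to contact, so about 16 interviews create little need to bring in known cases. Routes (a) and (b) already draw on the list of clinic attenders, so a known case at Imperial can be invited anyway. Only enrolment beyond that person's ordinary chance of responding is bias.

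Most of this stands. It removes any claim of deliberate choice, weakens the incentive and lowers the plausible size. It does not supply an approach rule, and it does not prevent a personal prompt in clinic from raising response among recognised cases.

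A reader might also infer that nothing at all would reveal the route. That goes too far. Online returns identify route (a), while (b) and (c) are described as paper. Section 3.1 is a list of study variables rather than operational logs, Appendix 1 is attached separately, and the content of Appendix 2 is not in the text available. What can be said is that the protocol lists no dedicated field, and that online versus paper cannot separate post from clinic or mark a recognised case.

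Finally, section 2 names no HAS mean, cut-off or prevalence, so the summaries used above are illustrative targets.

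**Conclusion.** The gap is real and inexpensive to close. The treating team makes the clinic approach with no consecutive-offer rule, clinician identification is one source of interviewees who must already be enrolled, and no listed variable or planned analysis would show whether recognised cases were over-represented.

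The size cannot be derived from the documents. On the assumptions of 20 recognised cases, all enrolling, 1.0 to 1.5 SD above average, the mean shift is about 0.08 to 0.20 SD at 150 returns. If those patients would have been invited anyway it is 0.08 to 0.12 SD, below the 0.16 SD half-width; only the surplus reading exceeds it, towards its upper end. At 350 returns the shift lies between zero and 0.09 SD.

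A reader might conclude that the primary result is inflated. The documents do not support that: they show a possible upward bias with no safeguard, and do not show that it occurs. Nor would a result without the recognised cases be the true one, because those patients belong to the clinic population.

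**What to change.** 1. In section 6, route (c), state that the study is offered to consecutive eligible attendees in each clinic session, regardless of suspected fear of hyperglycaemia.
2. Record for each participant the recruitment route (email, post, clinic), and whether a clinician had identified fear of hyperglycaemia before the questionnaire was completed.
3. In section 7, report the HAS summary by route, with a sensitivity row excluding clinician-identified participants. Label that row a lower bound with respect to this mechanism and not a corrected estimate.
4. Reconcile the two accounts of interview selection: section 4.1 and its repeat in section 6, against the sub-study text in section 6 and its repeat in section 7. State whether clinician identification is used and, if so, at what point.

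Cost: short text changes, two database fields and one small table, with no extra participants. Clinic staff lose some discretion over whom to approach and log slightly more data. The fields need to be collected as recruitment proceeds, because route and prior identification are hard to reconstruct reliably afterwards.
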